## Introduction

Class II malocclusion is one of major problems that patients seek orthodontic treatment. The dental and skeletal factors ranging from mild to severe provide the multiple characters of this malocclusion.

There are a number of orthodontic techniques and appliances for class II malocclusion treatment; among these are class II elastics. class II elastics correct a class II malocclusion by two actions: 1. maxillary retraction and clockwise rotation of the upper arch, and 2. mandibular arch protraction and clockwise rotation of the lower arch. This combination of anteroposterior and vertical effects corrects this malocclusion.

The force levels of elastics range from being light, medium, heavy and extra heavy. The force value of elastics should be provided by the manufacturers for different sizes. It is recommended to stretch the elastic to three times the original internal diameter to achieve the force stated on the package. the regular change of elastics is very important because their force level decreases rapidly. So effective use of elastics needs excellent patient cooperation.

In spite of their popularity, there are no significant data to determine the most convenient protocols to correct class II malocclusion with class II elastics. there are many variables related to class II elastics such the mode of elastics wear, the force value and change of elastics.

Several side effects have been attributed from the use of Class II elastics— eg, loss of mandibular anchorage, proclination of Lower incisors, extrusion of upper incisors, and even worsened smile esthetics due to increased gingival exposure.

According to the 20 principles of Alexander discipline, the premature use of class II elastics can be very dangerous if used with light arch wires that

cannot control torque. these elastics can cause proclination of the mandibular incisors, lingual tipping of maxillary incisors, mandibular molar extrusion and alteration of the occlusal plane. therefore, class II elastics should not be used until these factors under control. Alexander used 1/4 inch; 6 Oz elastics extended from maxillary lateral incisor ball hook to mandibular first or second molar which. Class II elastics Traditionally run from the upper canine hook to the lower first or second molar hook on stainless steel rectangular wire.

Sabrina Huang from Taiwan advocated use of the early light short elastics and she suggested the ELSE (Elastic, Light, Short and Early) acronym some years ago. Recently, the active early Protocol was introduced by Tom Pitts and Duncan Brown. This novel Protocol includes immediate light short elastics (ILSE) that allow the orthodontist to apply the elastics early from the first appointment. The authors mentioned the guiding principles of ILSE which include: shorter elastics is better than longer, full time wear, immediate elastics, lighter is better than heavier. They claim the active early Protocol is efficient, effective ad predictable producing outstanding results with more accurate and tightened slot. But these claims are based only on their case reports and clinical articles with no evidence based.

Therefore, the main objective of this study is to evaluate whether the use of immediate light short class II elastics can correct canine class II malocclusion without significant side effects when compared to the conventional longer and heavier elastics used with passive rectangular stainless-steel wire.

### **The review**

The correction of class II malocclusion By Intermaxillary elastics is one of the popular orthodontic techniques. In 1955 Tovstein used Class II elastics In both growing and non-growing patients. He found that non-growing Patients with the greatest growth had the least change in the inclination of the occlusal plane; conversely, patients with the least growth had the

greatest change in the occlusal plane. However, changes in inclination of the occlusal plane have a tendency to return to the original condition.

In 1984 Gianelly et al compared between Frankel, headgear and class II elastics for class II correction, The results indicate no treatment response that is uniquely related to a specific technique. 

In 1986 Meistrell et al used 1-2 oz class II elastics, he found that the maxillary first molar maintained it's anteroposterior position at the same time that SNA was reduced. The mandibular first molar moved forward by 1.2 mm. Vertical change in both the maxilla and the mandible were within normal ranges. No significant change in occlusal or mandibular plane angles was observed.

In 1999 Nelson et al used 1-2 oz class II elastics. He concluded that the changes contributing to Class II correction were mostly dental. Vertically, the net effects of treatment were increases in the mandibular plane angle and lower anterior facial height.

In 2006 Combrink et al elastics were successful for the correction of Class II discrepancies, promoting mainly dentoalveolar effects.

In 2007 Uzel et al compared between Class II elastics 3.5 oz 24 h/d and RMCC for treatment of Class II dental malocclusion, he found that both techniques are Effective for class II correction.

In 2008 Serbesis-Tsarudis and Pancherz compared between both class II elastics and herbest also in the same year Jones et al compared between class II elastics and forsus both authors found no significant differences between the elastics and the appliance.

Recently many authors like Tom Pitts and Duncan Brown published many case reports and clinical articles in which they claimed the effectiveness and efficiency of early light short elastics starting. also chris chang, Eugene Roberts and Linda Tseng.

So, class II elastics have been used for correction of both skeletal and dental class II for many years ago with different force levels, different amount of extension and different rate of elastics change.

### **Objective**

The aim is to compare the effect of immediate light short elastics versus conventional elastics on the Inclination of upper incisors in patients with canine class II malocclusion.

### **Methodology**

#### **Study population:**

This prospective clinical trial will be conducted on 30 patients both gender , divided into 2 groups:

Group 1: fifteen patients will wear immediate light short Class II elastics.

Group 2: fifteen patients will wear conventional elastics.

Selected from the outpatient clinic of the Orthodontic Department, Faculty of Dentistry, Ain Shams University.

The subjects will be selected to fulfill the following inclusion criteria:

- 1- Canine class II malocclusion.
- 2- Patients with permanent dentition.
- 3- Increased overjet.
- 4- Non extraction.

Exclusion criteria:

- 1- Gummy smile.
- 2- Gingival recession.
- 3- Vulnerable patients.

### **Study procedure:**

An informed consent will be signed by the patients' parents as well as an assent will be signed by young patients before their enrollment in the current study in which the aim of the study, the methodology and possible complications will be clearly described. This research will be reviewed by the Research Ethics Committee, Faculty of Dentistry, Ain Shams University.

Full orthodontic records will be taken for patients who meet the inclusion criteria. These records are:

- 1- Extra-oral and intra-oral photographs.
- 2- Orthodontic study casts.
- 3- Panoramic radiograph: will be used to detect any dental or bone anomalies.
- 4- Lateral cephalometric radiograph : for skeletal, dental and soft tissue assessment.

### **Procedure:**

- 1- The full orthodontic records will be taken for every patient.
- 2- The patients will be randomly allocated by computerized allocation.
- 3- The fixed orthodontic appliance including *0.018*" Bracket slot Roth prescription will be applied.

- 4- For both groups the disocclusion (disarticulation) will be done by adding glass ionomer luting cement at posterior Region that unlock the occlusion for greater freedom of teeth movements helping for easier and faster teeth movements.

The glass ionomer cement will be added at the central fossa of lower first molar to be more comfortable for patients.

Medicim glass ionomer luting cement will be used.

The disarticulation for group 1 will be done in the beginning of the treatment but in group 2 once Patients start to wear elastics at passive 0.016x0.022" stainless steel wire.

- 5- For group 1: the patients will be instructed immediately after bonding and initial wire placement to wear light short elastics from the upper first premolar to the lower first molar. The force level of elastics is within light range from 2oz - 3.5oz.
- 6- For group 2: the patients will be instructed to wear long elastics from the upper canine to the lower first molar, once the patients reach to 0.016x0.022" stainless steel passive wire. The force level of elastics is within medium range from 4oz -5oz.
- 7- The elastics force level will be measured every visit by gauge to ensure that it is within the range.
- 8- For both groups patients instructed and motivated to wear the elastics full time and change it every 12 hours . It is essential for the patient to demonstrate their ability to properly wear and remove the elastics before leaving the clinic.
- 9- Follow up charts will be given to the patients.
- 10- For both groups the following records will be taken before elastics wear and after, once patients reach to canine class I:
  - 1- The lateral cephalometric radiographs.
  - 2- Impressions For cast analysis.
  - 3- Standardized smile photographs.

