**Methods of assessment:**

- 1- Pre-operative T1 and postoperative T2 lateral cephalometric radiographs measures are compared and assessed.
- 2- Pre-operative and postoperative casts are compared and assessed.
- 3- Pre-operative and postoperative smile photographs are compared and assessed.
- 4- Calculation of The total period of elastics wear till the class I canine relationship achieved for both groups is compared and assessed.

	Outcome	Measuring tool	Measuring unit
Primary outcome	
 
• Upper incisor inclination (UI/PP) and (U1/SN).
 
• Upper incisors inclination and position (U1/NA)
 
	
 
• Lateral cephalometry.
 
• Lateral cephalometry.
 
	
 
• Degree
 
• Degree/mm
 

Secondary outcomes	
 
• Lower incisor inclination (LI/MP).
 
• Lower incisors inclination and position (L1/NB)
 
• Occlusal plane inclination (anatomical occlusal plane).
 
	
 
• Lateral Cephalometry
 
• Lateral cephalometry.
 
• Lateral cephalometry
 
	
 
• Degree
 
• Degree/mm
 
• Degree
 

--------------------	--	---	---

	
Op/(Me-Go) Op/FH Op/AB
 
 
• Mandible to cranial base (SNB)
 
• Mandible to cranial base (Pg to N perpendicular to FH).
 
• Maxilla to cranial base (SNA).
 
• Maxilla to cranial base (point A to N perpendicular to FH).
 
• ANB angle.
 
• FH, palatal and SN planes to mandibular plane angles.
 
• Ar Go Me
 
• ANS Me
 
• S Go
 
	
 
• Lateral cephalometry.
 
• Lateral cephalometry.
 
• Lateral cephalometry
 
• Lateral cephalometry.
 
• Lateral cephalometry.
 
• Lateral cephalometry.
 
• Lateral cephalometry.
 
• Lateral cephalometry
 
• Lateral cephalometry
 
	
 
• Degree
 
• mm
 
• Degree
 
• Mm
 
• Degree
 
• Degree
 
• Degree
 
• Mm
 
• mm
 

--	---	--	--

	

• Time of elastic wear

	Standardized extraoral photos	

• Months /days

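### T1 for the primary outcome is not tied to a film, and the most natural reading places it at different treatment stages in the two arms

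*Protocol*

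**What the plan says.** Methods of assessment, item 1, defines the comparison behind the primary outcome: "Pre-operative T1 and postoperative T2 lateral cephalometric radiographs measures are compared and assessed". Neither label is linked there to a visit or a procedure step.

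Two places in the protocol could supply T1.

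- **Entry records.** Procedure, step 1: "The full orthodontic records will be taken for every patient". The list under Study procedure shows that these include a film: "Lateral cephalometric radiograph : for skeletal, dental and soft tissue assessment". Allocation comes next, at step 2: "The patients will be randomly allocated by computerized allocation".
- **Records around elastic wear.** Procedure, step 10: "For both groups the following records will be taken before elastics wear and after, once patients reach to canine class I". The records are cephalograms, impressions for casts, and smile photographs.

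Elastics start at different stages. In group 1, "the patients will be instructed immediately after bonding and initial wire placement to wear light short elastics" (step 5). In group 2, "the patients will be instructed to wear long elastics from the upper canine to the lower first molar, once the patients reach to" the passive 0.016x0.022 inch stainless steel wire (step 6). Step 4 follows the same split: "The disarticulation for group 1 will be done in the beginning of the treatment but in group 2 once Patients start to wear elastics".

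**The concern.** A change score compares two arms fairly only if both start from the same point. A T1 film tied to the start of elastics would be close to untreated in group 1. In group 2 it would follow all the tooth movement needed to reach the passive rectangular wire. That movement can itself alter incisor inclination, which is the primary outcome.

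The two arms' change scores would then cover different parts of treatment, and their difference would mix the effect of the strategies with the unequal intervals. All secondary cephalometric outcomes use the same films and share the problem.

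**Working it through.** The protocol gives no SD, effect size or alignment change, so there is no figure to reproduce. The check sets the sections side by side and then uses simple algebra.

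**Step 1: which film is T1?**

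| Evidence | Points to |
|---|---|
| Step 10 is the only before/after pair of records in the Procedure | start of elastics |
| Its three record types match items 1 to 3 of Methods of assessment, in the same order | start of elastics |
| Smile photographs are named in step 10 and item 3, but not in the entry list | start of elastics |
| The term pre-operative can mean before any treatment | entry film |
| Entry records are also before elastics in both arms, so step 10 may only name which of them are repeated | entry film |

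The balance favours the start of elastics. It is not conclusive.

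**Step 2: when is a start-of-elastics film taken?** In group 1 it is no later than initial wire placement (step 5); it could be earlier, or could be the entry film itself. In group 2, if taken as elastics start, it comes at the passive rectangular wire (steps 4 and 6). The protocol does not list the intermediate wires, but reaching the passive wire implies them.

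**Step 3: effect on the comparison.** Write the mean changes in upper incisor inclination as:

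- a1, e1: the alignment and elastic components in group 1 up to canine Class I, which run concurrently;
- a2: group 2's change from bonding to the passive rectangular wire;
- e2: group 2's change from there to canine Class I.

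Assume that nothing moves in group 1 between the entry film and initial wire placement. Group 1's change is then a1 + e1 on either reading. The difference, group 1 minus group 2, is:

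- T1 = entry film: (a1 + e1) − (a2 + e2)
- T1 = start of elastics: (a1 + e1) − e2

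Subtracting the first from the second gives a2. The choice of T1 therefore moves the estimate one for one by group 2's mean change during alignment.

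**Step 4: would adjustment for T1 repair it?** No. On the start-of-elastics reading, group 2's T1 has already been changed by part of its assigned strategy and group 1's has not. The same T1 value describes an aligned patient in one arm and an essentially untreated one in the other.

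**The case against.** The strongest counter-argument concerns the question being asked. The Objective speaks of the effect of the elastics, and Methods of assessment, item 4, times the period of elastic wear. Measuring before and after elastics is a coherent answer to that question, though a non-randomised one. This stands in part: choosing the estimand is the sponsor's decision. But the start-of-elastics T1 does not isolate the elastics either, because a1 remains in group 1's change with no counterpart in group 2's. The closing paragraph of the Introduction also supports a strategy reading, since it contrasts immediate light short elastics with longer, heavier ones used on the passive rectangular wire.

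It can also be said that the harm is conditional, and that a statistical analysis plan might name the baseline. The first is true and limits the confidence. On the second, the timing of records is protocol text, stated in two sections that do not meet.

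A reader might infer three stronger things that the document does not support.

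- **That only group 2's T1 would follow randomisation.** A group 1 film at wire placement also follows allocation. The asymmetry is the treatment elapsed before T1.
- **That the baseline could be picked after the films are measured.** This presumes that group 2 has two separate pre-T2 films, which is an inference, and that no plan elsewhere fixes the choice.
- **That a shared entry film removes all bias.** T2 is taken when canine Class I is reached, a time that depends on outcome and may differ by arm.

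**Conclusion.** The point holds conditionally and should be fixed. The protocol leaves T1 undefined for its primary outcome. On the most natural reading, T1 falls at different treatment stages in the two arms.

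On that reading the between-arm difference is shifted by a2, group 2's mean change during alignment. The protocol does not allow its size or sign to be estimated, so no numerical bias is claimed. This rests on two assumptions: that T1 is the start-of-elastics film, and that group 1's incisors do not move between entry and initial wire placement. If T1 is the entry film in both arms, this particular distortion is absent and the defect is one of wording. Confidence is moderate because the text does not settle which reading is meant.

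**What to change.** Reconcile the Procedure with Methods of assessment:

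- For the primary and other cephalometric comparisons, define T1 in both arms as the lateral cephalogram in the full records taken at step 1, before allocation.
- Compare T2 between arms relative to that baseline, preferably adjusted for it.
- State that this compares the two strategies from the start of treatment.
- If group 2 has a separate film before elastics, report it only as an intermediate time point, in a secondary, non-randomised description of the elastic phase.

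**Cost.** Wording only. The film is already planned in both arms, so no radiographs, visits or patients are added.

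**Downside.** The contrast does not isolate the elastics, and a shared T1 leaves the outcome-dependent timing of T2 unchanged. Both should be acknowledged where the comparison is described.

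### Step 10 schedules the T2 records only at canine Class I, so a patient who stops without reaching it has no scheduled primary outcome measurement

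*Protocol*

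**What the plan says.** The Objective section states the aim: "The aim is to compare the effect of immediate light short elastics versus conventional elastics on the Inclination of upper incisors". The outcome table under Methods of assessment lists the primary outcomes, beginning with "Upper incisor inclination (UI/PP) and (U1/SN"), followed by U1/NA. All are measured on the lateral cephalogram.

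Item 1 of Methods of assessment gives the comparison: "Pre-operative T1 and postoperative T2 lateral cephalometric radiographs measures are compared and assessed". Step 10 of the Procedure gives the timing of the cephalogram, casts and smile photographs: "For both groups the following records will be taken before elastics wear and after, once patients reach to canine class I". Item 4 of Methods of assessment uses the same end point for duration: "Calculation of The total period of elastics wear till the class I canine relationship achieved for both groups is compared and assessed".

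From Study population to the end of the outcome table, the protocol sets no maximum wear time, no record at a fixed date, and no record on stopping or withdrawal.

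**The concern.** Patients are randomised at step 2, before the appliance is fitted. Whether they later reach canine Class I is a result of treatment. If T2 is tied to that result alone, the primary comparison is confined to patients whose treatment succeeded, and randomisation no longer fully protects it.

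Patients who do not reach Class I are foreseeable from the protocol itself:

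- Correction of the canine relationship by the test elastics is posed as an open question at the end of the Introduction.
- The Introduction also says "So effective use of elastics needs excellent patient cooperation".
- Step 8 asks a good deal of patients: "For both groups patients instructed and motivated to wear the elastics full time and change it every 12 hours".

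The bias could run either way. Poor cooperators may show little incisor change. Patients who stop because of an unwanted effect may show a lot, and theirs are the films a side-effect question most needs.

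**Working it through.** **Is there another route to T2?** Step 10 gives the only timing for the post-elastics records. Items 1 to 3 of Methods of assessment call them postoperative without adding a trigger, and item 4 follows wear only to Class I. The word *only* is thus an inference from the absence of any alternative. Three kinds of patient should be kept apart:

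- Reaches Class I: T2 is scheduled.
- Still wearing elastics and slow to respond: T2 remains due, because no maximum is set.
- Stops elastics, or ends study treatment, short of Class I: no T2 is scheduled.

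**Inputs.** From Study population: "This prospective clinical trial will be conducted on 30 patients both gender , divided into 2 groups", with 15 in each group. The protocol gives no failure rate, SD, target difference, alpha or power, so there is no figure of its own to reproduce. What follows is illustration under stated assumptions.

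**How likely is at least one such patient?** With an assumed rate p, the chance is 1 − (1 − p)^30.

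| Assumed p | Expected number of 30 | Chance of at least one |
|---|---|---|
| 5% | 1.5 | 78.5% |
| 10% | 3 | 95.8% |
| 20% | 6 | 99.9% |

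**How far could one arm's mean move?** Assume that k of 15 are lost in one arm and none in the other. Assume also that the tendency not to reach Class I and the incisor change are normal, with correlation r. The three largest expected order statistics for n = 15 are 1.7359, 1.2479 and 0.9477. The mean tendency among the 15 − k who remain is minus the sum of the top k divided by (15 − k):

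- k = 1: −1.7359/14 = −0.1240
- k = 2: −2.9838/13 = −0.2295
- k = 3: −3.9315/12 = −0.3276

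The shift in mean change, in SD units, is r times this. The standard error of the arm difference is √(1/15 + 1/(15 − k)).

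| k | Shift at r = ±0.25 | Shift at r = ±0.5 | SE | Shift/SE at r = ±0.5 |
|---|---|---|---|---|
| 1 (7%) | 0.031 | 0.062 | 0.372 | 17% |
| 2 (13%) | 0.057 | 0.115 | 0.379 | 30% |
| 3 (20%) | 0.082 | 0.164 | 0.387 | 42% |

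A positive r lowers the arm's mean and a negative r raises it. The shift is 0 at r = 0 and 0 when k = 0. It cancels between arms when both lose equally with the same r.

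**Cross-check.** If those who do not reach Class I differ by D SD from those who do, and the shares lost are f1 and f2, the bias is (f2 − f1) × D. With 0% against 20% and D from 0.5 to 1.0, this gives 0.10 to 0.20 SD, in line with the table.

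**Scale.** With 15 per arm, and an assumed two-sided 5% level and 80% power, the detectable difference is (1.960 + 0.842) × √(2/15) = 1.02 SD. The largest shift in the table is 0.164/1.02, or about one sixth of that. By normal approximation, the shifts at r = ±0.5 would raise the false-positive rate from 5% to about 5.3%, 6.1% and 7.1%.

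**The case against.** The strongest reply is that step 10 says when T2 is due and does not forbid records in anyone else. That is right as to wording. A reader might infer that patients who miss Class I *will* have no primary outcome, but the protocol supports only the statement that none is *scheduled* for them. An investigator might take a film anyway. It would be at discretion and might differ by arm.

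Second, incisor inclination is of interest as a side effect of correction, so measuring both arms at the same degree of correction is coherent. This stands, and the point does not dispute it.

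Third, a reader might infer that slow responders are lost. They are not, while they keep wearing elastics.

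Fourth, steps 7 to 9 support cooperation through force checks at each visit, motivation, demonstrated handling and follow-up charts. These lower the risk of failure without removing it.

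Fifth, the illustration puts all the loss in one arm. The arms do differ in force, elastic length and starting wire (steps 5 and 6), so equal loss cannot be taken for granted. Nothing in the protocol shows that it will be unequal either.

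Last, analysis sets and missing-data rules may sit in an analysis plan that is not shown. That is fair, and their absence is not the complaint. The timing of the primary measurement is a protocol matter, and no later plan can supply a missing cephalogram.

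**Conclusion.** The point holds as a gap in data collection: step 10 leaves patients who stop short of canine Class I without a scheduled T2, so the primary comparison is selected on a result that follows randomisation. It should be corrected before patients complete treatment, because the records cannot be recovered afterwards.

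The size is unknown. Under the assumed loss of 1 to 3 of 15 in one arm, with correlations of 0.25 to 0.5 in either direction, the shift is 0.03 to 0.16 SD. That is modest beside a detectable difference of about 1.02 SD. It is nil if all 30 reach Class I, or if the loss and its link with incisor change match across arms.

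Two stronger conclusions are tempting and not supported. One is that the trial will favour a particular arm: no failure rate, imbalance or direction is given. The other is that a common maximum wear time is required. Such a limit would mix incomplete correction into the primary comparison. It might also bind differently by arm, since group 1 starts elastics at the initial wire and group 2 only at the passive steel wire.

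**What to change.** Reword step 10 along these lines: *the records are taken before elastics are worn and again at canine Class I; if Class I is not reached, they are taken when elastics are permanently stopped or study treatment ends for any reason, and the date and reason are noted.* The second clause also covers a randomised patient who never starts elastics.

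Keep the comparison at Class I, and show beside it the comparison in all randomised patients with a T2. T2 in the added patients reflects shorter wear or incomplete correction, which is why both are needed.

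The cost is one sentence, a date field and a reason field. Each patient who does not reach Class I also has the second record set already planned for everyone, including one cephalogram: 1 to 3 films under the illustration. Some patients may be minors, so the consent and assent forms should mention this. Measurement is unchanged for patients who reach Class I. Patients lost to follow-up will still have no T2. Whether to add a common maximum wear time is for the sponsor to decide.
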